### 6.3. Description of Baseline Variables

Baseline demographic and clinical variables will be summarized for each of the treatment groups for the intention-to-treat (ITT), as treated (AT), and implanted sets. All continuous variables will be summarized as means, medians, standard deviations, interquartile ranges, minima and maxima and will be compared between treatment groups via 95% Bayesian credible intervals (BCIs) for the difference in means. Categorical variables will be summarized as frequencies and percentages and will be compared between treatment groups via 95% Bayesian credible intervals for the difference in proportions.

### 6.4. Kaplan-Meier Analyses

For safety related endpoints, the Kaplan-Meier event rates at 30 days, 6 months, 12 months, 18 months and annually through 10 years will be provided. For these analyses, these times correspond to 30 days, 183 days, 365 days, 545 days, 730 days, and annually through 10 years (365×3, 365×4, 365×5, etc.). At each time point with data, the product-limit estimate of the event rate, the number of subjects at risk, the number of subjects with events, the Peto standard error of the estimate, and the loglog transformed 95% confidence interval using the Peto standard error will be presented.

For subjects without an event, the date of censoring will be the latest date of all follow-up visits, assessments, and events (including death in those endpoints where death is not the endpoint).

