### 3.3.3.5. Secondary Safety Endpoints

- The rate of the composite of death, disabling stroke, life-threatening bleed, major vascular complications, or AKI (II or III) at 30 days
- The rate of new permanent pacemaker implantation at 30 days
- The rate of prosthetic valve endocarditis at one year
- The rate of prosthetic valve thrombosis at one year
- The rate of all stroke (disabling and non-disabling) at one year
- The rate of life-threatening bleeding at one year
- The rate of valve-related dysfunction requiring repeat procedure at one year

The incidence estimates for each endpoint above will be provided for the two treatment groups at the specified time point. The statistical method will be the Bayesian version of a comparison of proportions (with predictions). In addition, Kaplan-Meier estimates will be provided at the following time points: 30 days, 6 months, 12 months, and annually thereafter through 10 years.

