**Confidential**

## 5. Determination of Sample Size

### 5.1. Historical Data

Although the experience with surgical aortic valves in low surgical risk aortic valve replacement populations is extensive, it was not considered possible to leverage much of the data from these studies directly as surgical aortic valve replacement series typically enroll patient populations which include a proportion subjects with a bicuspid or unicuspid valve (excluded from this trial) which may be as high as approximately 50% and also include subjects with purely or primarily regurgitant lesions (also excluded from this trial) whose outcomes may differ from patients with aortic stenosis. As a result, series for which individual patient data were available or which were known to attempt exclusion of patients with bicuspid or unicuspid valves comprise the primary basis for the event rate estimate and additional series were considered only confirmatory in nature. Table 1 presents the rates of all-cause mortality at 24 months from studies which were considered in developing the event rate estimate. The simple weighted average from the studies was 11.4% which was adjusted up to 12% to account for the possibility that surgical candidates at extremely low risk (i.e. the healthiest and youngest potential subjects) may forego randomization into a TAVR trial until longer term data and data from lower surgical risk patients are available for TAVR.

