**Table 1. Surgical series supporting all-cause mortality event rate estimate**

Surgical Series	Number in Cohort	24-Month All-cause Mortality K-M Rate
NOTION SAVR cohort 	134	9.8%
3f Pivotal cohort 	405	12.7%
Mosaic sub-analysis 	646	9.9%
Freestyle sub-analysis 	323	13.5%
Simple Weighted Average	1508	11.4%
 Entire cohort leveraged (data on file)  Sub-group analysis excluding subjects <65 years of age, with congenital bicuspid valves or with a purely regurgitant lesion  Sub-group analysis excluding subjects <65 years of age, with congenital bicuspid valves, with a purely regurgitant lesion or with the Freestyle valve implanted as a full-root replacement		

The 24-month event rate estimate for non-fatal disabling stroke of 3% was generated primarily from the CoreValve US Pivotal High Risk Trial SAVR (3.9%) and TAVR (2.0%) cohorts which used event definitions consistent with this trial. Additional sources of data considered include the NOTION SAVR cohort (4.6%) and the Mosaic and Freestyle cohort sub-analyses (which had rates of 2.0% and 2.3% respectively) all of which collected clinical stroke/cerebrovascular accidents.

The incidence of the primary endpoint of all-cause mortality or disabling stroke at 24 months in each treatment group is expected to be 15%, which is based on an assumed rate of all-cause mortality of 12% at 24 months and a non-fatal disabling stroke rate of 3% at 24 months.

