## 6.7. Secondary Safety Endpoints

The following secondary endpoints will be compared between TAVR and SAVR subject cohorts using the appropriate Bayesian version of analysis for comparing proportions. In addition, Kaplan-Meier estimates will be provided.

- The rate of the composite of death, disabling stroke, life-threatening bleed, major vascular complications, or AKI (II or III) at 30 days
- The rate of new permanent pacemaker implantation at 30 days
- The rate of prosthetic valve endocarditis at one year
- The rate of prosthetic valve thrombosis at one year
- The rate of all stroke (disabling and non-disabling) at one year
- The rate of life-threatening bleeding at one year
- The rate of valve-related dysfunction requiring repeat procedure at one year

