## Notes:

1. DVI = Doppler Velocity Index (LVOT VTI/valve VTI)
  2. For subjects with BSA <1.6 m^2, the EOA criteria for significant (moderate or severe) stenosis is <0.6 cm^2
  3. For subjects with LVOT diameter >2.5 cm, the DVI criteria for significant (moderate or severe) stenosis is <0.2 cm^2
  4. Reporting of prosthetic valve dysfunction will be based on core lab results.
  5. Prosthetic valve dysfunction events are not reported as adverse events, unless the dysfunction is accompanied with clinical sequelae at the time of event detection, and the clinical sequelae are chronologically and physiologically associated with the dysfunction. However, prosthetic dysfunctions that are associated with adverse events, and that meet the definition of a serious adverse event, should be reported as such.
- Quality of Life as assessed by Kansas City Cardiomyopathy Questionnaire (KCCQ) at 30 days and one year  
The endpoint will be evaluated using a Bayesian analog of a two-sample t-test. Descriptive statistics for KCCQ change from baseline will also be reported at 30 days, 6 months, one year, and annually through 5 years.
  - The rate of repeat hospitalization for aortic valve disease at one year.  
The incidence estimate will be provided for the two treatment groups at the specified time point. The statistical method will be the Bayesian version of analysis for comparing proportions. In addition, the Kaplan-Meier estimates will be provided at the following time points: 30 days, 6 months, 12 months, 18 months, and annually thereafter through 10 years.
  - Device Success (VARC II), defined as
    - Absence of procedural mortality, AND
    - Correct positioning of a single prosthetic heart valve into the proper anatomical location, AND
    - Intended performance of the prosthetic heart valve, defined as the absence of patient-prosthesis-mismatch and mean aortic valve gradient less than 20 mmHg (or peak velocity < 3 m/sec), AND absence of moderate or severe prosthetic valve regurgitation.

The incidence estimate will be provided for the TAVR group.

The criteria for ECHO will be based on the ECHO Core Lab Data:

- Absence of patient-prosthesis-mismatch
  1. For subjects with BMI < 30 kg/m^2, index effective orifice area (EOAi) > 0.85 cm^2 /m^2
  2. For subjects with BMI ≥ 30 kg/m^2, index effective orifice area (EOAi) > 0.70 cm^2 /m^2

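### Kaplan-Meier rates to 10 years with death censored overstate how many patients actually have a late non-fatal event, so cumulative incidence should be reported alongside them

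*SAP*

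**What the plan says.** For safety-related endpoints SAP 6.4 states that "the Kaplan-Meier event rates at 30 days, 6 months, 12 months, 18 months and annually through 10 years will be provided". A patient without the event is censored at the latest visit, assessment or event on record, "including death in those endpoints where death is not the endpoint". The product-limit result is presented as the event rate.

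Protocol 3.3.3.5 lists the secondary safety endpoints: the 30-day composite, new pacemaker, endocarditis, valve thrombosis, all stroke, life-threatening bleeding, and valve dysfunction requiring a repeat procedure. It adds that "Kaplan-Meier estimates will be provided at the following time points: 30 days, 6 months, 12 months, and annually thereafter through 10 years". SAP 6.8 sets the same kind of schedule for repeat hospitalization: "30 days, 6 months, 12 months, 18 months, and annually thereafter through 10 years".

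The formal comparison of the secondary safety endpoints is separate. Under SAP 6.7 they are "compared between TAVR and SAVR subject cohorts using the appropriate Bayesian version of analysis for comparing proportions", at 30 days or 1 year, and the Kaplan-Meier estimates are additional.

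The continued-access SAP (7.3) repeats the rule of censoring at death. Neither the protocol nor either SAP mentions competing risks or a cumulative incidence function.

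**The concern.** A patient who has died can no longer have a stroke, a valve thrombosis or a repeat valve procedure. If deaths are censored, one minus Kaplan-Meier estimates the risk in a hypothetical cohort in which nobody dies. That is a legitimate quantity, but it is not the share of treated patients who have the event, and the gap widens as deaths accumulate.

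The follow-up is long enough for this to matter. Patients are followed for 10 years, and the plan assumes 12% mortality in the first two. After 1 year, Kaplan-Meier is the only prespecified estimate for the secondary safety endpoints and for repeat hospitalization. Repeat valve procedure is the most sensitive case: its long-term rate bears directly on durability in low-risk patients, and a death-censored figure labeled as an event rate is easily read as a patient's actual risk. If survival differs between TAVR and SAVR, the overstatement also differs by arm.

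**Working it through.** **Inputs from the documents**
- Two-year mortality: "an assumed rate of all-cause mortality of 12% at 24 months" (SAP 5.1). The four surgical series in Table 1 range from 9.8% to 13.5%.
- Two-year non-fatal disabling stroke: 3% (SAP 5.1), used below as an example of a non-fatal event.
- Horizon: 10 years.

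**Reproducing the plan's figure.** The weighted average in Table 1 is (134×9.8 + 405×12.7 + 646×9.9 + 323×13.5)/1508 = 17212.6/1508 = 11.4%. This matches the SAP, which then adjusts the figure up to 12%.

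**Assumptions not in the documents.** The documents give no mortality or event rates at 10 years. The base case assumes that the mortality hazard and the event hazard are both constant for 10 years, with an event hazard of 1% per year.

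**Formulas.** With λd the death hazard and λe the event hazard:
- λd = −ln(1 − 0.12)/2 = 0.0639 per year; λe = 0.01 per year.
- Kaplan-Meier with death censored: 1 − exp(−λe·t).
- Cumulative incidence: [λe/(λe+λd)] × [1 − exp(−(λe+λd)·t)].

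**At 10 years**
- Kaplan-Meier: 1 − exp(−0.10) = 9.5%.
- Cumulative incidence: (0.01/0.0739) × (1 − exp(−0.739)) = 0.1353 × 0.5225 = 7.1%.
- Ratio 1.35. The implied 10-year mortality, leaving events aside, is 1 − 0.88⁵ = 47%.

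The same formulas give ratios of 1.03 at 1 year, 1.065 at 2 years and 1.17 at 5 years.

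**With the plan's 3% event rate at 24 months** in place of 1% per year, the 10-year figures are 14.1% against 10.5%, a ratio of 1.34.

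**Sensitivity of the 10-year ratio** (event rate 3% at 24 months unless stated; 12% two-year mortality unless varied)

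| What is varied | Ratio |
|---|---|
| Two-year mortality 6% (assumed) | 1.16 |
| Two-year mortality 9.8% (lowest series) | 1.27 |
| Two-year mortality 13.5% (highest series) | 1.39 |
| Mortality hazard rising 8% per year | 1.42 |
| 3% operative deaths, then constant hazard | 1.30 |
| All events within 30 days | 1.003 |
| 90% of the two-year event hazard within 30 days | 1.11 |
| 50% of the two-year event hazard within 30 days | 1.28 |
| Events only in the first 2 years | 1.06 |
| Event hazard rising linearly (0.003 × years) | 1.50 |

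The direction is the same in every row. The size depends mainly on when the events occur.

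**The case against.** A reader might infer that all non-fatal endpoints are overstated by about a third at 10 years. The documents do not support that. Their mortality figures stop at 24 months, and the 12% was itself adjusted upward. A third requires both that mortality and a constant event hazard to persist for a decade. New pacemaker, a 30-day endpoint that Protocol 3.3.3.5 nevertheless carries to 10 years, is likely to cluster around the procedure, and its ratio would be close to 1.

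Nor can a reader conclude that the trial's inferences are compromised. The secondary safety endpoints are compared as proportions at 30 days or 1 year, and even a Kaplan-Meier figure at 1 year would be only about 3% too high in relative terms. The primary endpoint includes death. None of the ordered labeling tests in SAP 6.9 uses these estimates. This objection stands in full, and it confines the point to descriptive long-term tables.

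The case for keeping Kaplan-Meier also stands. Cumulative incidence depends on mortality as well as on the event. With the same event hazard (3% at 24 months), the 10-year cumulative incidence is 11.1% at 9.8% two-year mortality and 10.1% at 13.5%, while Kaplan-Meier is 14.1% in both. An arm with more deaths would thus appear to have fewer valve events. For comparing durability the death-censored figure has a proper use, so replacing it would be a choice of estimand rather than a correction.

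It can also be said that the SAP names its estimator and prints the numbers at risk, so an informed reader is not misled. This answers only part of the point, because no figure for patients' actual risk is planned beside it.

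Finally, the general rule in continued-access SAP 7.3 might suggest that every endpoint there is affected. The specific text is narrower. Addendum 8.1 limits reporting after 1 year to mortality, all stroke and repeat procedure, and Addendum 11.5 plans annual estimates to 10 years for those same events. Continued-access SAP 7.7 names only mortality or all stroke after 1 year.

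**Conclusion.** The point holds for late, descriptive estimates. As written, the plan will report 2-to-10-year rates of non-fatal events that are higher than the proportion of patients who have them, and it offers no companion estimate that accounts for death.

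Under the constant-hazard base case the 10-year figure is 2.4 percentage points too high (9.5% against 7.1%). Over the Table 1 mortality range the ratio is 1.27 to 1.39, using the 3% two-year event rate, and it falls to 1.16 if two-year mortality is only 6%. Event timing moves it further, from about 1.0 for purely periprocedural events to about 1.5 for events with a rising hazard, as late re-intervention may have. All these figures extend two-year planning rates to 10 years by assumption. The direction does not depend on that assumption; the size does.

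**What to change.** Amend SAP 6.4, and the matching text in SAP 6.7 and 6.8, as follows:
- For every endpoint that does not include death, report the Aalen-Johansen cumulative incidence with death as a competing event, with its confidence interval, alongside the Kaplan-Meier estimate at each time point from 2 years on.
- Use the cumulative incidence when describing patients' actual long-term risk.
- Label the Kaplan-Meier figure as the death-censored estimate.

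In the continued-access study, make the same addition for all stroke and repeat valve procedure, the non-fatal events followed beyond 1 year.

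The cost is SAP wording, one standard procedure and an extra column in the long-term tables. Dates of death are already collected. Sample size, type I error and the primary analysis do not change. Specifying this before the late data are seen also avoids choosing the estimator afterwards.

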### 6.5. Primary Objective

The primary endpoint of all-cause mortality or disabling stroke at 24 months will be evaluated using the absolute difference of the TAVR rate and the SAVR rate for all-cause mortality or disabling stroke during a fixed follow-up of 24 months. The hypothesis test is designed to show non-inferiority of TAVR to SAVR for the primary endpoint.

#### 6.5.1. Hypothesis of non-inferiority

The primary objective is to establish that TAVR is non-inferior to SAVR for the primary endpoint. The hypothesis of interest is:

$$H: \pi_T < \pi_C + \delta$$

where  $\pi_T$  and  $\pi_C$  respectively denote incidence of all-cause mortality or disabling stroke at 24 months for the treatment (TAVR) and control (SAVR) groups, and  $\delta = 0.06$ . This study is designed using Bayesian statistical techniques. TAVR will be considered to be non-inferior to SAVR if it can be established that the posterior probability  $\Pr(H_{\delta=0.06} | \text{data}) > \Psi$ , where  $\Psi$  is a pre-specified threshold value. In addition, the primary endpoint (superiority) will be tested according to the testing order specified in Section 6.9. The values chosen for  $\Psi$  and  $\Psi_{\text{SUP}}$  are chosen to ensure type I error rates are not larger than 0.05 for non-inferiority and 0.025 for superiority.

This document is electronically controlled. Printed copies are considered uncontrolled.

**Confidential**

### 6.5.2. Analysis Plan

The two interim analyses and final analysis are planned when:

1. 850 subjects have had the chance to be followed for 12 months (12 months after the 850th procedure date);
2. 1200 subjects have had the chance to be followed for 12 months (12 months after the 1200th procedure date);
3. All subjects have had the chance to be followed for 24 months (24 months after the last LTI subject's procedure date).

At the first interim analysis, the posterior probability of non-inferiority  $P(H_{\delta=0.06} | \text{data})$  will be calculated, and if this probability exceeds a pre-specified threshold  $\Psi$ , non-inferiority will be concluded. This will be considered an “early win” for non-inferiority, and a regulatory submission will follow. Otherwise, follow-up will continue until the second interim analysis, where again the posterior probability of non-inferiority  $P(H_{\delta=0.06} | \text{data})$  will be calculated, and if this probability exceeds a pre-specified threshold  $\Psi$ , non-inferiority will be concluded and a regulatory submission will follow. If non-inferiority is not concluded at either of the interim analyses, follow-up will continue until all subjects have had the chance to be followed for 24 months (24 months after the last LTI subject's procedure date), and non-inferiority will be tested a third time. The standard for concluding non-inferiority in each case is the same:  $P(H_{\delta=0.06} | \text{data}) > \Psi$ .

If non-inferiority is established at either interim analysis, a test of superiority may be performed (See Section 6.9 for additional requirements and testing sequence). If  $P(H_{\delta=0} | \text{data}) > \Psi_{\text{SUP}}$ , superiority will be established at this time. However, if  $P(H_{\delta=0} | \text{data}) \leq \Psi_{\text{SUP}}$ , subjects will continue to be followed until the full cohort has had the chance to be followed for 24 months (24 months after the last LTI subject's procedure date), at which time a delayed determination of superiority may be made if  $P(H_{\delta=0} | \text{data}) > \Psi_{\text{SUP}}$ .

If non-inferiority is not established until the final analysis, then superiority will only be tested at that time per the testing sequence outlined in Section 6.9.

The maximum number of non-inferiority assessments is three (first interim analysis, second interim analysis, final analysis). The maximum number of superiority assessments is two (simultaneous to passing the non-inferiority assessment for the primary endpoint and the hierarchical testing for the secondary endpoints listed in Section 6.9, or at the final analysis in the event that superiority is not established at one of the interim analyses).

The statistical approach for these analyses is Bayesian. The prior distributions for  $\pi_T$  and  $\pi_C$  in these calculations are Beta(1,1). In each analysis (interim or final), any subject with missing 24-month outcome will have that outcome predicted via a Bayesian piecewise exponential survival model that incorporates follow-up to date. Within a treatment group, let a subject's time to event follow a piecewise exponential model whose hazard function  $\lambda(\tau)$  is piecewise constant over the 3 partitioning intervals defined by the cutoff points 0, 30 days, 183 days, and 730 days. The parameters for each of the 3 intervals are assigned diffuse Gamma prior distributions, with mean 1 and variance 100, which at the time of analysis are updated based on observed data, and unobserved 24-month outcomes are predicted with probabilities determined by this model. Combining predicted and observed 24-month outcomes and integrating out the predictive distributions results in a posterior probability of non-inferiority (or superiority) that accounts for missing data as well as the uncertainty in the prediction, and this is the quantity that is compared to  $\Psi$  (or  $\Psi_{\text{SUP}}$ ) to assess non-inferiority (or superiority). This approach is similar to that taken in the SURTAVI trial, though in this case the statistical model underlying the predictions is based on a time-to-event model rather than a set of beta-binomial models. It is also similar to the approach taken in Wilber et al. The thresholds  $\Psi$  and  $\Psi_{\text{SUP}}$  are selected empirically to achieve a type I error rate (under extensive simulation) of at most 0.05 for non-inferiority testing and at most 0.025 for superiority testing.

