### 3.3.3.4.2 Randomization

Randomization will follow a 1:1 (treatment:control) allocation ratio and be stratified by site and need for revascularization, using a blocked randomization scheme with blocks of randomly varying sizes. The sample size for the AT population is 1200 subjects. The first interim analysis (timed to occur when 850 subjects are followed for 12 months) will be conducted for the purpose of possibly passing the primary objective. If the criterion for passing the primary objective is not met at this time, the second interim analysis (timed to occur when 1200 subjects are followed for 12 months) will again be conducted for the purpose of possibly passing the primary objective. If non-inferiority is not concluded at either of the interim analyses, follow-up will continue until all subjects have reached 24 months (24 months after the last LTI subject's procedure date), and a final analysis will occur.

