### 3.3.4 Number of Subjects and Investigational Devices, Trial Duration

This trial will involve at least 1200 subjects in the AT population among all active sites. No site will implant more than 100 subjects without prior authorization from Medtronic. Subjects who exit from the trial after implantation will not be replaced.

Subjects will be consented for follow-up through 10 years. The enrollment period is estimated to be between 18 to 24 months; therefore the estimated total duration of the trial (first subject enrolled to last subject completing his/her last follow-up exam) is estimated to be 12 years. The number of investigational TAVR systems used in the trial is estimated to be between 600 and 700 (based on sample size and 1:1 randomization).

Randomization will continue until the required number of subjects in the LTI Sub-Study and the Japan addendum are met, up to 1540 randomized subjects.

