8. Subjects confirmed eligible for implantation by the Screening Committee will be randomized in a 1:1 fashion to either TAVR or SAVR, stratified by site and the need for coronary revascularization during SAVR. Coronary artery bypass graft (CABG) should be conducted during the index procedure. Concomitant percutaneous coronary intervention (PCI)v and TAVR is encouraged; however staging is left to the discretion of the operator. Intervention/repair of the mitral and/or tricuspid valve is only

---

iiiIf a subject has balloon aortic valvuloplasty after their qualifying TTE, they must have repeat TTE to confirm he/she meets criteria for severe aortic stenosis as described in Section 3.3.5.1 prior to submission to the screening committee.

[figure not shown]
iv Anatomical suitability will be confirmed by Medtronic Screening Lab. Information on MDCT procedures and sizing recommendations is provided in Appendix II, Section 4.0.

v Index PCI should be performed at the TAVR implanting center; index PCI operators will be considered investigators.

allowed if deemed necessary during the SAVR procedure, but there must be no intent to do this type of intervention/repair prior to implant.

9. Trial randomization will not be blinded. Once randomization is complete and a treatment arm is assigned, crossover from SAVR to TAVR treatment is not permitted. The sponsor will strictly monitor device dispensation to ensure that only those subjects randomized to the Medtronic TAVR treatment arm receive the Medtronic TAV. Distribution of the subjects within the trial groups will be controlled at the implanting sites by means of central randomization using interactive voice/web randomization service (IXRS). The randomization scheme will be securely stored at the IXRS provider.
10. Implantation should occur within 90 days of Screening Committee approval.
11. Subjects who consent to participate in the LTI study will also follow the LTI sub-study protocol as described in APPENDIX VII: LEAFLET THICKENING/IMMOBILITY SUB-STUDY PROTOCOL

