**Two Year (between 730 and 760 days post-implant)**

- Clinical assessment
- TTE
- Modified Rankin Score
- KCCQ
- Anti-thrombotic medications
- I.N.R. (for subjects on VKA)
- Adverse Events

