### Notes

1. TTE, MDCT, coronary arteriography, or labs performed for diagnostic purposes prior to consent may be used for the baseline/screening exams, provided they were performed within window and contain the necessary data.
2. Only the sites participating in the LTI Sub-study will consent for both the main study and LTI Sub-study.
3. Subjects who give consent for LTI Sub-study will follow sub-study protocol in addition to main protocol.

This document is electronically controlled. Printed copies are considered uncontrolled.

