## 7. Additional Analysis

There will be approximately 50 AT subjects from Japan in this study. Once the primary objective demonstrates non-inferiority (either at one of the interim analyses, or at the final analysis), an additional report specifically for these Japanese subjects will be prepared as requested by PMDA, which includes descriptive statistics for the primary endpoint and all secondary endpoints. In addition, poolability analysis (Japan vs. non-Japan data) will be performed.

---

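### The final analysis is timed from the last LTI sub-study subject, so the plan does not guarantee 24 months of follow-up for every as-treated subject

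*SAP*

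**What the plan says.** The third planned look in SAP 6.5.2 takes place when "All subjects have had the chance to be followed for 24 months (24 months after the last LTI" subject's procedure). Protocol 3.3.3.4.2 is worded more strongly: "follow-up will continue until all subjects have reached 24 months (24 months after the last LTI subject's procedure date"). SAP 2 and protocol 3.3.3.4.3 repeat the LTI anchor. SAP 6.5.2 and protocol 3.3.3.4.3 apply it also to the delayed superiority test, where it is meant to represent the full cohort.

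The end of accrual follows a different rule. Protocol 3.3.4 states: "Randomization will continue until the required number of subjects in the LTI Sub-Study and the Japan addendum are met, up to 1540 randomized subjects". SAP 7 expects a Japanese contingent: "There will be approximately 50 AT subjects from Japan in this study".

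LTI participation is voluntary and limited by site. The notes to the flow diagram in SAP 4 say: "Only the sites participating in the LTI Sub-study will consent for both the main study and LTI Sub-study". Protocol 3.3.8 leaves a gap between approval and treatment: "Implantation should occur within 90 days of Screening Committee approval".

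**The concern.** Accrual closes when two conditions are met, but the final analysis is timed from only one of them. If the LTI requirement is filled first and randomisation goes on for Japan, the last treated subjects are not LTI subjects, and 24 months from the last LTI procedure comes too early for them. The issue is not confined to Japan. Even if the last randomised subject is an LTI subject, a non-LTI subject approved earlier can be treated later, because up to 90 days may pass between approval and procedure.

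What is at stake is the basis of the last non-inferiority look and of the delayed superiority look. No later look would correct either. Subjects short of 24 months would enter both with predicted outcomes, although the plan describes the cohort as fully followed.

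**Working it through.** **The rules side by side.**

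- First interim: 12 months after the 850th procedure (SAP 6.5.2, protocol 3.3.3.4.3). The anchor is a count of treated subjects.
- Second interim: 12 months after the 1200th procedure. The anchor is of the same kind.
- Final: 24 months after the last LTI procedure. The anchor is a sub-study.
- End of randomisation: LTI and Japan requirements both met, capped at 1540 (protocol 3.3.4).

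The final trigger covers everyone only if the last LTI procedure is also the last AT procedure. No text says so, and none says that Japanese subjects belong to the LTI sub-study or are treated before it closes.

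**The plan's own sample size.** This shows whether the trigger date enters it. Inputs from SAP 5.2: 15% in each arm, margin 0.06, alpha 0.05 (taken as one-sided), power 85%. In the Farrington-Manning method the constrained null rates are 0.1248 (control) and 0.1848 (TAVR).

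- s0 = √(0.1248×0.8752 + 0.1848×0.8152) = 0.5098
- s1 = √(2×0.15×0.85) = 0.5050
- n per arm = [(1.645×0.5098 + 1.036×0.5050)/0.06]² = 515.2, rounded up to 516, so 1032 in total, as stated
- 1032/0.94 = 1098 (stated as 1100), and 1200/1100 = 1.09, the stated 9%

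The date of the final analysis appears in none of these steps. Moving the anchor leaves 1032, 1100 and 1200 unchanged.

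**Size of the possible gap.** The documents give no lag between the last LTI procedure and the last AT procedure, so the lag L is an assumption, shown over a range. Further assumptions: all 50 Japanese subjects trail by the full L, and the hazard is constant with 15% of subjects having an event by day 730.

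- h = −ln(0.85)/730 = 0.0002226 per day
- Expected events still to come at the trigger = 50 × [exp(−h(730 − L)) − 0.85]

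| L (days) | Unobserved events among 50 |
|---|---|
| 30 | 0.28 |
| 90 | 0.86 |
| 180 | 1.74 |
| 365 | 3.60 |

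Total expected events are 0.15 × 1200 = 180. The unobserved share is therefore between 0.28/180 = 0.2% and 3.60/180 = 2.0%. The result scales with the number of trailing subjects: ten subjects trailing by 90 days would leave 0.86/5 = 0.17 events unobserved.

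**The case against.** The strongest reply is that the main clause, which speaks of all subjects, governs, and the parenthesis only shows how it was expected to be met. LTI sites may number up to 100 worldwide (protocol Appendix VII, 4.2), which equals the site cap for the whole trial including Japan (protocol 3.2.1). Japanese subjects may therefore be LTI subjects, or may be treated before the sub-study closes, and then the gap is nil. SAP 6.5.2 also predicts any missing 24-month outcome at every look, using follow-up to date and carrying the uncertainty into the posterior. The same method supports interim looks at which some subjects have only about 12 months of follow-up. All of this stands. It limits the consequence, but it does not make the two rules agree. The parenthesis is the only operational definition of the date, and it can conflict with the clause it explains.

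Two stronger readings are tempting and are not supported.

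- **Visit window.** A reader might infer from the two-year visit, "Two Year (between 730 and 760 days post-implant", that subjects treated in the last month have not reached 24 months at the trigger. The SAP fixes 24 months at day 730 in the per-protocol definition (6.2.2), the Kaplan-Meier times (6.4) and the last cut point of the prediction model (6.5.2). Twenty-four calendar months are 730 or 731 days, so anyone treated on or before the last LTI procedure date has reached that point. An open window only delays ascertainment.
- **A share of roughly 4 to 8%.** A reader might count a final month's accrual, 1200/24 = 50 to 1200/18 = 67 subjects, and add the 50 Japanese subjects. That runs from 50/1200 = 4.2% to (67 + 50)/1540 = 7.6% of the cohort. It requires a data cut on the trigger day, whereas SAP 6.5.3 speaks of database lock without fixing it to that day. It also requires every Japanese subject to trail and the average accrual rate to hold in the last month. The documents give none of these.

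**Conclusion.** The point holds as an unguaranteed rule. It does not establish that subjects will in fact fall short. The trigger delivers 24 months for the whole AT set only if the last LTI subject is the last subject treated. Protocol 3.3.4, the voluntary nature of LTI participation and the 90-day allowance all permit otherwise.

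The effect on the primary result is probably small: about 0.3 to 3.6 unobserved events out of about 180. That range rests on an assumed lag of 30 to 365 days, on all 50 Japanese subjects trailing, and on a constant hazard at the planned 15% rate. It does not cover other non-LTI subjects treated late, whose number the documents do not give. Sample size and power are unaffected. The correction is still worth making because it concerns the final confirmatory looks and costs little.

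**What to change.** In SAP 2, at each mention in SAP 6.5.2 (the list of looks, the non-inferiority paragraph and the delayed superiority paragraph), and in protocol 3.3.3.4.2 and 3.3.3.4.3, replace the reference to the last LTI subject with: *24 months after the procedure date of the last AT subject, from any source (LTI, Japan or other)*. This puts the final look on the same kind of anchor as the two interims.

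The cost is a change of wording and a delay equal to the time, if any, between the last LTI procedure and the last AT procedure. If the two coincide, there is no delay.

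A separate and optional clarification is to state whether database lock waits for the two-year visit window to close. A trigger at day 760 is not needed for subjects to reach 24 months.
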